5 STUDY POPULATION

5.1 Number of Subjects (approximate)

Approximately 50 subjects will be screened in order to enroll approximately 30 subjects.

5.2 Study Population Characteristics

Subjects of at least 18 years of age of either sex and any race, with a diagnosis of dry eye disease, who meet all of the inclusion criteria and none of the exclusion criteria.

5.3 Inclusion Criteria

General/Ocular Inclusion Criteria

1. Will be at least 18 years of age at the time of consent.
2. Able to provide written voluntary informed consent.
3. Have a subject-reported history of DED in both eyes for at least 6 months prior to Visit 1.
4. Have Tear film break-up time (TFBUT) <10 sec at Visit 1.
5. Have Meibomian Gland Dysfunction (MGD) defined as total MGD score ≥ 3 (secretion of 5 central glands on lower eyelid will be evaluated, each will be scored from 0-3; 0 = normal, 1 = thick/yellow, whitish, particulate 2 = paste; 3 = none/occluded; total score will range from 0-15) at Visit 1.
6. Have a total corneal fluorescein staining score of ≥ 2 and ≤ 11 (i.e. sum of inferior, superior, central, nasal, and temporal) according to the National Eye Institute (NEI) scale at Visit 1.
7. Have at least one eye that satisfies all criteria for 4-6 above at Visit 1.
8. Is able to fix his/her gaze for a minute, i.e. can see the fixation target and with no nystagmus
9. Is able and willing to follow instructions, including participation in all trial assessments and visits.

Confidential

5.4 Exclusion Criteria

General/Ocular Exclusion Criteria

1. Have any clinically significant ocular surface slit-lamp findings at Visit 1 and Visit 2 and/or in the opinion of the Investigator had any findings that may have interfered with trial parameters, including
 - a. history of eye trauma
 - b. history of Stevens-Johnson syndrome
 - c. active blepharitis or lid margin inflammation
 - d. DED secondary to scarring, irradiation, alkali burns, cicatricial pemphigoid, or destruction of conjunctival goblet cells (as with vitamin A deficiency).
 - e. abnormal lid anatomy that caused incomplete eyelid closure
 - f. corneal epithelial defect or significant confluent staining or filaments
 - g. abnormal cornea shape (keratoconus)
 - h. history of herpetic keratitis.
 - i. has a pterygium in either eye.
 - j. ocular or periocular rosacea that in the judgement of the Investigator interfered with the trial
2. Has used any topical ocular steroids treatments, prescription dry eye therapy including varenicline nasal spray, or topical anti-glaucoma medication within 60 days prior to Visit 1.
3. Have had a LipiFlow procedure within 1 month prior to Visit 2.
4. Have received a permanent punctum plug within 3 months (6 months for dissolvable punctum plugs) prior to Visit 2. Have removed a permanent punctum plug within 1 month prior to Visit 2.
5. Have used any eye drops (prescription or artificial tears) and/or TrueTear™ device (intranasal tear neurostimulator) within 24 hours before Visit 2.
6. Have active ocular allergies or ocular allergies that are expected to be active during the trial period.
7. Have worn contact lenses within 1 month of Visit 1 or anticipate using contact lenses during the trial.
8. Have undergone intraocular surgery or ocular laser surgery within the previous 6 months or had any planned ocular and/or lid surgeries over the trial period.
9. Have an active ocular or systemic infection (bacterial, viral, or fungal), including fever requiring treatment with antibiotics.
10. Is a woman who was pregnant, nursing or planning a pregnancy.
11. Is a woman of childbearing potential who is not using an acceptable means of birth control; acceptable methods of contraception included: hormonal (oral, implantable, injectable, or transdermal contraceptives); mechanical (spermicide in conjunction with a barrier such as a diaphragm or condom); intrauterine device; or surgical sterilization of partner. For non-sexually active females, abstinence could have been regarded as an adequate method of birth control; however, if the subject becomes sexually active during the trial, she must agree to use adequate birth control as defined above for the remainder of the trial.
12. Has an uncontrolled systemic disease in the opinion of the Investigator will interfere with the trial.
13. Has a known allergy and/or sensitivity to the investigational drug or saline components.
14. Has used any oral medications known to cause ocular drying (eg, antihistamines, antidepressants, etc.) on a non-stable regimen within 1 month prior to Visit 1 or is expected to be unstable during the trial.
15. Have taken isotretinoin (e.g. Accutane, Myorisan, Claravis, Amnesteem) within 6 months of Visit 1
16. Has corrected VA worse than or equal to logarithm of the minimum angle of resolution (LogMAR), +0.7 as assessed with Early Treatment Diabetic Retinopathy Study (ETDRS) charts in both eyes at Visit 1.

17. Is currently enrolled in an investigational drug or device study or had used an investigational drug or device within 60 days of Visit 2.

5.5 Withdrawal Criteria (if applicable)

Subjects may voluntarily withdraw from the study at any time.

Additionally, subjects may be discontinued for safety reasons as determined by the investigator (see Section 8.6.2).

6 STUDY PARAMETERS

6.1 Efficacy Measures and Endpoints

6.1.1 Primary Efficacy Measure(s) and Endpoints

- Change from baseline in mucus-aqueous layer thickness (MALT) and thinning rate (MALTR) for study eyes at 5 ± 1 min, 15 ± 2 min, 30 ± 2 min, 60 ± 5 min, 120 ± 10 min, and 240 ± 10 min following instillation of NOV03

6.1.2 [REDACTED]

[REDACTED]

[REDACTED]

[REDACTED]

[REDACTED]

6.2 Safety Measures

- Adverse Events (AEs; reported, elicited and observed)

7 STUDY MATERIALS

7.1 Study Treatment(s)

7.1.1 Study Treatment

PFHO drug product is a thin, clear, preservative-free ophthalmic drop (see [Table 1](#)). PFHO must be stored in a secure area accessible only to the investigator or pharmacist and his/her designees. PFHO must be stored **at room temperature** under temperature- monitored conditions and must not be refrigerated.

Table 1 Active Investigational Product

	Investigational Product
Product code:	NOV03 (MIEBOT TM)
Chemical name:	Perfluorohexyloctane (PFHO)
Molecular formula:	C ₁₄ H ₁₇ F ₁₃
Dosage form:	3 mL ophthalmic solution
Unit dose:	11 µL drop size; 100% perfluorohexyloctane
Route of administration:	Topical ocular administration
Physical description:	Colorless and clear ophthalmic solution
Excipients:	None
Manufacturer:	[REDACTED] [REDACTED]

7.1.2 Instructions for Use and Administration

- At Visit 2, a designated clinical staff member will instill 1 drop of the investigational product into each eye:

7.2 Other Study Supplies

- Questionnaires, Urine Pregnancy Tests, sterile cotton-tipped swab (for MGD assessment), Schirmer's test strips, sodium fluorescein.

8 STUDY METHODS AND PROCEDURES

8.1 Subject Entry Procedures

8.1.1 Overview

Subjects as defined by the criteria in sections 5.2, 5.3, and 5.4 will be considered for entry into this study.

8.1.2 Informed Consent

Following identification of a potential subject, the Investigator (or designee) will explain the purpose of the study, procedures, risks/benefits, and subject responsibilities to the potential subject. The subject's willingness and ability to meet the follow-up requirements of the study will be determined. If the subject chooses to participate in the investigation, written informed consent will be obtained. The subject and the person obtaining written consent will sign and date the IRB-approved ICF, at which point the subject is considered part of the study population. The original signed document will be retained in the subject records, and a copy will be provided to the subject. In addition, the applicable privacy regulation requirements must be met.

8.1.3 Washout Intervals

Subjects will adhere to the following medication washout intervals during the period indicated **prior to Visit 1 or 2 as indicated** and will refrain from using these medications during the study:

24 Hours

Artificial tears, topical ocular prescription eye drops, True Tear device, lid scrubs, lid wipes, warm compresses within 24 hours of Visit 2 (Assessments)

1 Month

- contact lenses within 30 days of Visit 1 (Screening)
- oral medications known to cause ocular drying (e.g. antihistamines, antidepressants etc) on a non-stable regimen with 30 days of Visit 1 (Screening)
- Lipiflow within 30 days of Visit 2 (Assessment)
- Removed a punctal plug within 30 days on Visit 1 (Screening)

2 Months

- Topical steroids, cyclosporine, lifitegrast, serum tears, glaucoma medication within 60 days of Visit 1 (Screening)

3 Months

- Received a permanent punctum plug within 90 days of Visit 2 (Assessment)

6 Months

- Received or removed a dissolvable punctum plug within 6 months of Visit 2 (Assessment)
- Have taken isotretinoin (e.g. Accutane, Myorisan, Claravis, Amnesteem) within 6 months of Visit 1 (Assessment)

8.1.4 Procedures for Final Study Entry

Subjects must meet all of the inclusion criteria and none of the exclusion criteria in order to be enrolled in the study.

8.2 Concurrent Therapies

The use of any concurrent medication, prescription or over-the-counter, is to be recorded on the subject's source document and corresponding case report form (CRF) along with the reason the medication was taken.

Concurrent enrollment in another investigational drug or medical device study is not permitted.

8.2.1 Prohibited Medications/Treatments

Refer to Section 8.1.3 for a complete list

8.3 Examination Procedures

8.3.1 Procedures to be Performed at Each Study Visit

Refer to Appendix 2 for details on the ocular assessments.

8.3.1.1 VISIT 1 (Day -14 to Day -1): Screening/ Informed Consent/ Eligibility

- Informed Consent/HIPAA: Prior to any changes in a subject's medical treatment and/or study visit procedures, the study will be discussed with each subject and subjects wishing to participate must give written informed consent and sign a HIPAA form.

In the event that a subject has a medical condition, medication/contact lens washout, or needs to speak with the Investigator prior to Visit 1, the subject will be given an informed consent form. Medical/medication history, demographics, and inclusion/exclusion review may be performed at the time of informed consent signing prior to Visit 1, but must be confirmed at Visit 1.

- Demographic data and medical/medication/ocular and non-ocular history: Collect and record all demographic data, medical history, any medications, and any underlying condition(s). Current underlying conditions, including those that began within the last 30 days, which may have been resolved before screening must be recorded. Record any medications the subject is taking, as well as those the subject may have taken but discontinued within 60 days prior to Visit 1.
- Review of Inclusion/Exclusion Criteria: A review of protocol inclusion and exclusion criteria will be confirmed for each subject.
- Urine Pregnancy Test (for females of childbearing potential): Females of childbearing potential must have a negative urine pregnancy test to continue in the study and must agree to use an acceptable method of contraception throughout participation in the study.
- Ocular Surface Disease Index (OSDI®) questionnaire
- Visual acuity (ETDRS)
- Slit-Lamp biomicroscopy
- Tear Film Break-up Time (TFBUT)
- Fluorescein staining (NEI scale)
- Meibomian gland assessment (MGD score) (wait 5 min prior to start of Schirmer's test)
- Schirmer's test I (without anesthesia)
- Intraocular pressure
- Adverse Event Query
- Schedule Visit 2: Qualifying subjects will be scheduled to return to the office for Visit 2.

8.3.1.2 VISIT 2 (Day 1)

- Update of Medical/Medication History
- Slit-Lamp biomicroscopy (wait ~20 min prior to TFI baseline measurements)

- Baseline Tear Film Imager assessments (2 measurements made 20-40 min apart)
- Instillation of study drug
- Post-instillation Tear Film Imager assessments (at 5, 15, 30, 60, 120 and 240 min following PFHO instillation)
- Adverse Event Query
- Study Exit

8.4 Schedule of Visits, Measurements and Dosing

8.4.1 Scheduled Visits

Refer to Appendix 1 for a schedule of visits and measurements.

If a subject is discontinued at a scheduled study visit, the remaining assessments should be captured on the Unscheduled Visit/Early Exit Visit pages of the Source Document and corresponding CRF.

8.4.2 Unscheduled Visits

For Unscheduled Visits, the reason for the visit should be clearly documented on the appropriate CRF, including findings from all evaluations that are completed.

These visits may be performed to ensure subject safety. All information gathered at unscheduled visits should be recorded on the Unscheduled Visit/ Early Exit Visit pages of the Source Document and corresponding CRF.

8.5 Compliance with Protocol

Subjects who are inappropriately enrolled may be discontinued from the study. The reason for such discontinuation will be recorded as “protocol violation” in the source document and on the appropriate page in the CRF.

Site staff will review concomitant medication use at each visit. Any new medication (or) changes in existing concomitant medication use will be recorded in the source document and on the Concomitant medication CRF.

8.6 Subject Disposition

8.6.1 Completed Subjects

A completed subject is one who has not been discontinued from the study.

8.6.2 Discontinued Subjects

Subjects may be discontinued prior to their completion of the study due to:

- subject request/withdrawal
- AEs
- protocol violations

- administrative reasons (e.g., inability to continue, lost to follow up)
- sponsor termination of study
- other

Note: In addition, any subject may be discontinued for any sound medical reason.

Notification of a subject discontinuation and the reason for discontinuation will be made to the sponsor and will be clearly documented on the CRF.

8.7 Study Termination

The study may be stopped at any time by the investigator or the sponsor with appropriate notification.

8.8 Study Duration

This trial consists of 2 office visits over a period of approximately 2 weeks.

8.9 Monitoring and Quality Assurance

Audits of clinical research activities in accordance with the Bausch + Lomb's internal Standard Operating Procedures (SOPs) to evaluate compliance with the principles of GCP may take place. A regulatory authority may also wish to conduct an inspection (during the study or after its completion). If an inspection is requested by a regulatory authority and/or IRB, the Investigator must inform Bausch + Lomb immediately that this request has been made.

9 ADVERSE EVENTS

9.1 Definition of Adverse Event (AE)

An adverse event is any untoward medical occurrence in a subject participating in a clinical study, which does not necessarily have a causal relationship with the study product/procedure. Therefore, an adverse event includes:

- Any unfavorable and/or unintended sign (including an abnormal laboratory finding), symptom, or disease onset, that occurs at any time between the signing of the ICF and study exit, without any judgement about causality (i.e., whether or not it is considered to be related to the study product)
- Exacerbation, worsening, or progression of a pre-existing illness, including an increase in severity, frequency, and/or duration of a pre-existing episodic event or condition
- Events occurring from drug overdose (accidental or intentional), drug abuse or misuse, drug hypersensitivity, drug extravasation, drug interactions, drug dependency, events occurring from drug withdrawal and medication errors
- A condition detected or diagnosed after study product administration even though it may have been present prior to the start of the study

A treatment-emergent adverse event (TEAE) is defined as an AE with a start date on or after the first dose of study drug, or that worsened following administration of study drug.

An AE does not include the following:

- Medical or surgical procedures (e.g., surgery, endoscopy, tooth extraction, transfusion) as event terms; the condition that led to the procedure is the AE if it meets the definition of an AE.
- Situations where an untoward medical occurrence has not occurred (e.g., hospitalization for cosmetic elective surgery; and social and/or convenience admissions).

Symptoms associated with disease, which are consistent with the subject's usual clinical course; unless the subject experiences worsening of their symptom(s) or the symptom(s) meet the criteria for an SAE.

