9.3 General Guidelines for Reporting Adverse Events

It is the responsibility of the investigator to document all AEs that occur during the course of the study. Throughout the study, efforts will be made by the investigator to remain alert to possible AEs. The period of observation for collection of AEs extends from the time the subject gives informed consent until the last study visit or discontinuation from the study. The first concern will always be the safety of the subject, and appropriate medical intervention will be made.

The AEs should be documented as a single medical diagnosis. When this is not possible, the AE should be documented in terms of signs and/or symptoms observed by the investigator or reported by the subject at each study visit. Each AE which appears to be independent of any prior event will be reported separately.

All AEs occurring after the subject signs the informed consent through the last study visit must be reported, regardless of whether or not the AEs are considered drug-related. All AEs, whether in response to a query, observed by the study site personnel, or reported spontaneously by the subject, will be recorded. Any AEs deemed related to treatment reported or observed at the final study/treatment visit will be followed until stabilization or resolution (or up to 30 days after final study visit).

At each visit during the study, the subject will be assessed for the occurrence of new and ongoing AEs. Tolerability signs and symptoms that result in the subject's requiring a concomitant therapy, interruption of treatment, or discontinuation from the study will be reported as an AE. The following data will be collected on all AEs and recorded on the appropriate CRF:

- Event name (diagnosis preferred, if unknown, record the signs/symptoms)
- Onset date and end date
- Maximum intensity (severity)
- Seriousness
- Action taken regarding study drug
- Corrective treatment/therapy, if given
- Outcome

- Resolution

The investigator will also provide an assessment of the causal relationship to the study drug (for pre-treatment AEs, causality is “not related”). Rationale MUST be provided for any “not related” assessment and is recommended for “related” assessments.

All AEs must be reported regardless of whether the AEs are considered drug-related.

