10.2.1 Adverse Events

Adverse events (AEs) will be coded using the MedDRA dictionary. Frequencies and percentages of treatment-emergent adverse events (TEAEs) will be summarized at the subject level by system organ class and preferred term for all TEAEs, treatment related TEAEs, and serious TEAEs. An AE is treatment emergent if it occurs or worsens after the first dose of study medication. Similar summaries will be presented for all TEAEs by maximal severity. Separate summaries will be performed for ocular and non-ocular AEs.

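### Do two wordings of the treatment-emergent rule, with an onset date but no onset time, leave Day 1 adverse events unclassifiable?

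*Combined protocol and SAP*

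**What the plan says.** Section 9.1 gives the first definition: "A treatment-emergent adverse event (TEAE) is defined as an AE with a start date on or after the first dose of study drug", with a second limb for an event "or that worsened following administration of study drug".

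Section 10.2.1 gives the second: "An AE is treatment emergent if it occurs or worsens after the first dose of study medication". It asks for tables "for all TEAEs, treatment related TEAEs, and serious TEAEs", and adds: "Similar summaries will be presented for all TEAEs by maximal severity".

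Section 9.3 sets the collection period: "The period of observation for collection of AEs extends from the time the subject gives informed consent until the last study visit", or until discontinuation. The only timing item in its list of adverse event data is "Onset date and end date". It also has a rule that depends on the order of event and dose: "for pre-treatment AEs, causality is" fixed as not related.

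Section 8.3.1.2 puts the slit-lamp examination and two baseline imaging measurements before the single instillation on Day 1. The post-instillation imaging, the adverse event query and study exit follow at the same visit.

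**The concern.** One analysis term has two definitions, and nothing says which governs. Section 9.1 speaks of a start *date* and includes events *on* the dose. Section 10.2.1 does neither.

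In a trial lasting weeks this would touch few events. Here there is one dose, and routine collection ends at the visit where it is given; only serious events are reportable for a further 30 days (Section 9.2). Nearly every event that could be treatment-emergent therefore carries the dosing date, and that is the date on which the wordings can diverge.

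The data list appears to make this worse, because an onset date cannot separate an event during the baseline measurements from one after the drop. Adverse events are the only safety measure, so the all-event and maximal-severity tables could include events that the drug cannot have caused, or omit some that it did.

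**Working it through.** **Inputs.** The two definitions (Sections 9.1 and 10.2.1); the onset-date field and the pre-treatment causality rule (9.3); the Visit 2 sequence (8.3.1.2); the imaging windows (6.1.1); about 30 subjects (5.1). The plan states no figure to reproduce here.

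**Step 1: the definitions side by side.** Suppose the order of onset, worsening and dose is known, and ask whether each kind of event counts as treatment-emergent.

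| Event | 9.1, clock time | 10.2.1, clock time | 9.1, calendar day |
|---|---|---|---|
| Onset before Day 1, no worsening | No | No | No |
| Onset Day 1 before the drop, no worsening | No | No | Yes |
| Onset Day 1 after the drop | Yes | Yes | Yes |
| Onset before the drop, worse after it | Yes | Yes | Yes |

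The clock-time columns are identical. The calendar-day reading of 9.1 differs in one row only.

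**Step 2: direction of error if only the date is used.** Section 9.1 by calendar day counts every Day 1 event, which over-counts the second row. A strict date-level *after* in 10.2.1 would drop every non-worsening Day 1 event, including those in the third row, which under-counts. So the error could run either way. But Section 10.2.1 does not mention dates, and reading it by date would nearly empty the tables it specifies. That is a strong reason not to read it so.

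**Step 3: how long the ambiguous interval is.** Scheduled time at Visit 2 before the drop is about 20 + (20 to 40) = 40 to 60 minutes. Scheduled time after it is 240 ± 10 = 230 to 250 minutes. The pre-drop share runs from 40/(40 + 250) = 13.8% to 60/(60 + 230) = 20.7%. This is a share of scheduled minutes, not of events, and it leaves out any part of Day 1 before the visit.

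**Step 4: which tables are exposed.** A pre-drop event that the investigator identifies is *not related* by rule, so it stays out of the treatment-related table. The serious table would need a serious event that began before the drop in a subject who was still dosed. That leaves the all-event and maximal-severity tables.

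**Step 5: size per subject.** For a misclassified subject with no other treatment-emergent event, the change in the any-event percentage is 1/n.

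- n = 30: 1/30 = 3.3 points; two subjects, 2/30 = 6.7 points.
- n = 27 to 33 (an assumed ±10% around the approximate enrolment): one subject, 1/33 = 3.0 to 1/27 = 3.7 points; two, 2/33 = 6.1 to 2/27 = 7.4 points.

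These figures apply to any miscounted subject. They say nothing about how often it would happen, and the documents give no rate.

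**Step 6: what else fixes the order of event and dose.** Site staff instil the drop (7.1.2), and its time must be known to meet windows as tight as 5 ± 1 minutes (6.1.1). Investigators must recognise pre-treatment events to apply the 9.3 causality rule, and must give a rationale for every not-related judgement (9.1.2, 9.3). Records must be contemporaneous (11.6). The onset-date field is therefore not the only information available.

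**The case for a change.** The best case for a change is that one analysis term should not have two definitions, least all in a study where nearly every relevant event falls on the dosing date. The only adverse event query listed for Visit 2 comes after the last imaging assessment, so events from before and after the drop may be elicited together hours later. The 9.3 causality rule assumes that the order is known but does not itself record an onset time. Aligning the sentences, with at most one extra field, would cost little.

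Some of this stands. The wordings do differ, and the listed date field alone cannot order Day 1 events under either definition. An event that a subject recalls only at the final query may be hard to place.

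The step from there to unreliable tables does not stand. It needs an analyst to apply calendar dates mechanically and ignore the investigator's pre-treatment judgement. The exposed group is also narrow: onset on Day 1 before the drop, no later worsening, and no other treatment-emergent event in that subject. Section 9.1 excludes symptoms in line with the subject's usual course, and exclusion criterion 1 would keep some subjects with significant slit-lamp findings from being dosed. Finally, the case report form is not among the documents, so a missing time field cannot be asserted.

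**Conclusion.** No change to the plan is needed. The difference between Sections 9.1 and 10.2.1 is one of drafting, and the absent onset time is a detail that the site and the analysts can supply. Read in the ordinary sense, with the dose as a moment, both sections count onset or worsening once the drop has been given.

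The number of events at risk is unknown, probably very small and possibly zero. Each affected subject with no other treatment-emergent event would shift one descriptive percentage by about 3.3 points at n = 30. Every such event is still recorded, whichever table it enters. There is no second arm to bias, and the efficacy tests and sample size do not depend on it.

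This rests on two assumptions: that Day 1 events are classified by their order relative to the drop, not by date alone, and that the investigator's identification of pre-treatment events is available to the analyst. Matching the two sentences at a future revision would be tidy, but the safety conclusions do not depend on it.
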